7.2.9. Pharmacodynamic Parameter Analyses

If data permit, the following plasma PD parameters will be calculated in the Treatment Period for the Week 6 (Day 43) and Week 36 (Day 253) Visits using noncompartmental methods for total Cu and PUF Cu (measured and absolute change from Baseline) concentrations with Phoenix[®] WinNonlin[®] (Certara USA Inc., Princeton, New Jersey) version 8.0 or higher or SAS[®] version 9.4 or higher (SAS Institute Inc., Cary, North Carolina), as applicable. Calculations will be based on the actual sampling times relative to the actual reference ALXN1840 dosing times recorded during the study.

- E_{max} : maximum observed PD concentration in plasma
- TE_{max} : time to reach maximum observed PD concentration in plasma
- $AUEC_t$: AUEC from time 0 to last quantifiable concentration time, calculated using the linear trapezoidal rule

Additional PD parameters may be calculated, as necessary.

Parameters for total Cu and PUF Cu in plasma will be summarized separately using descriptive statistics. Geometric mean and geometric %CV will be calculated for AUECs and E_{max} .

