7.2.5.1. Pharmacokinetic and Pharmacodynamic Sampling

In the Treatment and Extension Periods, plasma samples will be obtained from the blood samples collected pre-dose on the day of all study visits. Patients will be instructed not to take their dose of ALXN1840 on the morning of scheduled study visits, so that PK/PD/biomarker samples are collected at pre-dose trough for measuring total and PUF Mo (PK), total and PUF Cu, cNCC/NCC_{corrected}, dNCC, LBC (PD), Cp, and CpC (biomarker). Additional measurements on ALXN1840 PK/PD including Mo and Cu in the tripartite complexes (TPCs) may be conducted.

In the Treatment Period, at the Week 6 (Day 43) and Week 36 (Day 253) Visits, serial blood samples will be collected for plasma PK/PD/biomarker concentrations at the following time points: pre-dose at 0 hour, and at 2- and 4-hours post-dose.

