7.2.5.3. Pharmacokinetic/Pharmacodynamic Data Presentation Conventions

Pharmacokinetic and PD concentration data will be summarized using the following descriptive statistics: number of patients (N), number of patients with available data (n), arithmetic mean, SD, arithmetic coefficient of variation (arithmetic CV), geometric mean (GM), GMCV, median, minimum, and maximum.

The pre-dose PD concentration will be used as Baseline; the absolute change from Baseline will be calculated as: a post-dose concentration value – Baseline concentration value; and the percent change from Baseline will be calculated as: $([\text{a post-dose concentration value} - \text{Baseline concentration value}] / \text{Baseline concentration}) \times 100\%$.

The following conventions will be applied to PK/PD presentations and summaries.

- For continuous variables, all mean and median values are formatted to 1 more decimal place than the measured value. SD values are formatted to 2 more decimal places than the measured value. Minimum and maximum values are presented with the same number of decimal places as the measured value.
- Date variables are formatted as DDMMYYYY for presentation. Time is formatted in military time as HH:MM for presentation.

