9.4.5. Baseline

Baseline is defined as the last assessment yielding non-missing valid values taken prior to the first dose of study drug. The same Baseline will be used for both Treatment Period and Extension Period.

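### SAP 7.2.9 asks for geometric means of change-from-Baseline copper parameters that can be zero or negative, and SAP 7.2.5.3 does not say which pre-dose sample is Baseline

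*SAP*

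**What the plan says.** SAP 7.2.9 (Pharmacodynamic Parameter Analyses) plans Emax, TEmax and AUECt at the two profile visits, Week 6 (Day 43) and Week 36 (Day 253), if data permit. The parameters are computed for "total Cu and PUF Cu (measured and absolute change from Baseline) concentrations". AUECt is defined as "AUEC from time 0 to last quantifiable concentration time, calculated using the linear trapezoidal rule". SAP 7.2.5.1 sets the sampling times at those visits: "pre-dose at 0 hour, and at 2- and 4-hours post-dose".

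SAP 7.2.9 gives two instructions for summarising the parameters. The first is general: "Parameters for total Cu and PUF Cu in plasma will be summarized separately using descriptive statistics". The second adds to it: "Geometric mean and geometric %CV will be calculated for AUECs and" Emax. The second makes no distinction between the measured scale and the change scale.

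Baseline is described in more than one place. SAP 9.4.5 says: "Baseline is defined as the last assessment yielding non-missing valid values taken prior to the first dose of study drug". SAP 7 gives the same rule for all assessments. SAP 7.2.5.3, the convention for PK/PD data, says: "The pre-dose PD concentration will be used as Baseline". It names no visit.

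**The concern.** A geometric mean is the exponential of the mean log, so it needs strictly positive values. Measured concentrations meet that condition apart from zeros. Changes from Baseline do not: a linear-trapezoid area computed on changes carries a sign, and so does the maximum of a set of changes. A programmer following 7.2.9 literally would meet values with no logarithm and would have to leave them out or invent a rule. If they are left out, the geometric mean describes only patients whose parameter was positive, and it cannot be anything but positive.

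The Baseline wording adds a second uncertainty. Measured from the last value before the first dose, the change at Week 6 or Week 36 is the cumulative effect of treatment. Measured from that visit's own 0-hour sample, it is a four-hour within-day effect from an on-treatment trough. These are different quantities and can differ in sign. At stake is whether these tables describe plasma copper at the two profile visits correctly and reproducibly.

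**Working it through.** The documents give no figure for this point, so there is none to reproduce. The check has three parts.

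**1. Do other rules fill the gap?** SAP 7.2.6 and 7.2.8 discard values of 0 when a geometric mean is calculated. That rule is written for concentrations, is not repeated in 7.2.9 and does not mention negative values. SAP 7.2.8 has an explicit rule for negative cNCC, but nothing comparable exists for change-scale AUECt or Emax. SAP 7.2.5.2 sets all BLQ values to 0 for PUF Cu parameter calculations, so low values stay in the profile and can give zero or negative changes. The gap is not closed elsewhere.

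**2. What does each Baseline reading give?** For changes c0, c2 and c4 at 0, 2 and 4 h:

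- AUECt = 2(c0 + c2)/2 + 2(c2 + c4)/2 = c0 + 2c2 + c4
- Emax = max(c0, c2, c4)

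The profiles below are assumed for illustration, with a Day 1 value of 1000 in arbitrary units.

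| Profile (0/2/4 h) | Baseline | Changes | Emax | AUECt |
|---|---|---|---|---|
| 700/760/720 | Day 1 | -300, -240, -280 | -240 | -300 - 480 - 280 = -1060 |
| 700/760/720 | visit 0 h | 0, 60, 20 | +60 | 0 + 120 + 20 = +140 |
| 900/1020/950 | Day 1 | -100, 20, -50 | +20 | -100 + 40 - 50 = -110 |
| 900/1020/950 | visit 0 h | 0, 120, 50 | +120 | 0 + 240 + 50 = +290 |
| 1200/1150/1100 | Day 1 | 200, 150, 100 | +200 | 200 + 300 + 100 = +600 |
| 1200/1150/1100 | visit 0 h | 0, -50, -100 | 0 | 0 - 100 - 100 = -200 |

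The first and third profiles change the sign of AUECt in opposite directions when the Baseline changes. In the second, with Day 1 as Baseline, Emax has a logarithm and AUECt does not, so the two parameters would be summarised over different patients. With the visit's own 0-hour sample as Baseline, c0 is always 0. Emax then cannot be negative, but it is exactly 0 whenever both later samples are lower.

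**3. How many patients could be affected?** The documents give no expected direction or SD for the change in plasma total Cu or PUF Cu, so this is a range under assumptions: Day 1 Baseline, normal changes, between-patient SD of 1, independent within-profile SD of 0.3 at each time, and 400,000 simulated patients per scenario. Counts use the 24 planned evaluable patients for scale only.

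| True mean change (SD) | AUECt ≤ 0 | of 24 | Emax ≤ 0 | Geometric mean of positive AUECt/4 h (SD) |
|---|---|---|---|---|
| -1 | 84% | 20.1 | 77% | 0.33 |
| -0.5 | 69% | 16.5 | 59% | 0.42 |
| 0 | 50% | 12.0 | 40% | 0.54 |
| +0.5 | 31% | 7.5 | 23% | 0.72 |
| +1 | 16% | 3.9 | 11% | 0.97 |

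The AUECt column can be checked in closed form. The time-averaged change (c0 + 2c2 + c4)/4 has SD √(1 + 0.09 × 6/16) = √1.03375 = 1.017, so the share at or below zero is Φ(-m/1.017). This is 0.163 at m = +1 and 0.837 at m = -1. The positives-only geometric mean is above zero in every row, including the row with a true mean of -1 SD.

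**The case against.** The strongest reply is that nothing is concealed. The geometric statistics come on top of the ordinary descriptive statistics in 7.2.9, and SAP 7 sets arithmetic mean, SD, median, minimum and maximum as the default for continuous variables. Those accept negative values. SAP 7.2.8 also lists, summarises and plots measured values, change and percent change for total Cu and PUF Cu, and SAP 7.2.4 fits an MMRM to change and another to percent change. A reader might infer that a fall in copper would be hidden. The documents do not support that: it would show in all of these outputs.

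A reader might also infer that the plan drops every patient whose copper fell. No such instruction exists; exclusion follows from taking logs. It would also not reach every such patient: with Day 1 as Baseline, Emax is lost only if all three samples are at or below Baseline, and with the visit's own 0-hour sample a patient well below Day 1 can still have positive parameters.

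On Baseline, a reader might infer that the SAP states two conflicting definitions. It does not quite do so. Protocol Table 1 schedules a PK/PD sample on Day 1, collected before dosing, and read that way 7.2.5.3 agrees with SAP 7 and 9.4.5. But 7.2.5.1 describes a pre-dose sample at every visit, so the wording does not single out Day 1.

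Finally, the direction of change is not given. Protocol 4.2 describes mobilisation of drug-copper-albumin complexes, and SAP 7.2.8 confirms that such complexes carry copper in plasma on treatment, so a rise in total Cu is plausible. That is a fair limit on the size of the problem. It does not make a geometric mean defined for a non-positive value.

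**Conclusion.** The point holds as a specification gap with limited reach. The text of 7.2.9 covers change-scale AUECt and Emax in its request for geometric mean and geometric %CV, these statistics are undefined at or below zero, and no rule covers negatives. Any figure produced would be conditional on a positive value. The Baseline wording in 7.2.5.3 is ambiguous; one reading conflicts with SAP 7 and 9.4.5, and the choice can change the sign of the parameters.

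The size cannot be computed from the documents. The ranges of 16% to 84% for AUECt and 11% to 77% for Emax rest on the normality, the SDs, the Day 1 Baseline and the span of mean changes assumed above.

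These are descriptive, exploratory PD parameters with no hypothesis test. The primary liver Cu analysis and its power do not depend on them.

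**What to change.** In SAP 7.2.9, limit geometric mean and geometric %CV to AUECt and Emax derived from measured concentrations. Summarise the change-from-Baseline versions by arithmetic mean, SD, median and range only, over all patients with the parameter.

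In SAP 7.2.5.3, state that Baseline is the last valid value before the first dose of study drug, as in 9.4.5. If the within-visit change from that day's pre-dose sample is also wanted at Weeks 6 and 36, present it separately under its own label.

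The cost is SAP wording and table shells. No additional data or sampling is needed.

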7.3. Safety Analyses

All safety analyses will be conducted on the Safety Analysis Set in the Treatment Period. Safety analyses will include all AEs, ECGs, clinical laboratory data, physical examinations, and vital sign measurements using descriptive statistics. By-patient listings will also be provided. No formal hypothesis testing is planned.

The verbatim terms as reported in the CRF by Investigators to identify AEs will be coded using MedDRA version 23.0 or higher and summarized by primary SOC and PT.

7.3.1. Study Duration, Treatment Compliance, and Exposure

Study duration will be summarized for all enrolled patients. Treatment compliance and exposure will be summarized for the Safety Analysis Set.

Study duration is defined as the time from the first dose to the end of the main study period (i.e., Week 48 for patients who do not go into the Extension Period or up to Week 96 for patients in the Extension Period) or study discontinuation date, whichever occurs first.

Compliance to the study treatment regimen will be determined as the number of days the study drug is taken / the number of days the study drug is expected to be taken during active study

treatment $\times 100$. Treatment compliance will be summarized using descriptive statistics. Compliance up to Week 48 will be shown for all patients. Patients who enter the Extension Period will also have their compliance calculated up to Week 96 and only for the duration of the Extension Period from Week 48 to Week 96. If a patient discontinues prematurely from the study, his or her compliance will be based on the period up to the point of discontinuation from the study. Compliance will also be summarized using counts and percentages by compliance category (i.e., $\geq 100\%$ compliance, 80% to $< 100\%$ compliance, and 60% to $< 80\%$ compliance).

Study drug administration data will be presented in a by-patient listing. The start and end dates for a dose and frequency for each patient will be presented.

Extent of exposure to study drug will be summarized. The duration of exposure will be presented in days and calculated as the last dose of study drug - the first dose of study drug + 1. Duration of exposure, average daily dose (mg), minimum daily dose (mg), and maximum daily dose (mg) will be summarized using descriptive statistics.

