2.2.2. ALXN1840

ALXN1840 (bis-choline tetrathiomolybdate; formerly known as WTX101) is a novel, first-in-class, Cu-protein binding agent in development for the treatment of WD.

ALXN1840 has been selected for development in WD due to its improved stability properties over ammonium tetrathiomolybdate, which has previously been studied in patients with WD and

other indications. Ammonium tetrathiomolybdate as well as bis-choline tetrathiomolybdate non-clinical and clinical data reported to date support the efficacy and safety of ALXN1840.

ALXN1840 has been evaluated in 28 patients with WD in an open-label Phase 2 Study WTX101-201. Results from the main 24-week study showed that ALXN1840 monotherapy reduced mean serum non-ceruloplasmin-bound Cu (NCC) by 72% at Week 24 compared with baseline. ALXN1840 treatment also resulted in significant improvements in neurological status and disability measured as a change from baseline in Unified WD Rating Scale (UWDRS) Part III and Part II, respectively. In addition, liver status, as measured by the Modified Nazer Score and model for end-stage liver disease (MELD), was stabilized or improved in most patients. Treatment with ALXN1840 was generally well-tolerated, with most reported AEs being mild (Grade 1) to moderate (Grade 2). Reversible liver function test elevations were observed in 39% of patients; these elevations were mild to moderate, asymptomatic, were associated with no notable increases in bilirubin (ie, no documented case of Hy's Law), and normalized with dose reduction or treatment interruption. No paradoxical neurological worsening was observed upon treatment initiation with ALXN1840 (Weiss, 2017). All patients who completed the 24-week Initial Dosing Period were enrolled in a 36-month Extension Period to assess long-term efficacy and safety of ALXN1840.

Preliminary PK data at 48 weeks from the Extension Period of the study were consistent with the 24-week Dosing Period results. No clear dose-proportionality was observed in Study WTX101-201. This result may have been due to the small sample size and relatively high inter-patient variability.

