2.3.1. Risk Assessment

Details of the potential risks and mitigation strategy are provided in [Table 3](#). Further information on ALXN1840 is available in the IB.

Table 3: Potential Risks and Mitigation Strategy

Potential Risk of Clinical Significance	Summary of Data/Rationale for Risk	Mitigation Strategy
ALXN1840		
Anemia	Anemia has been observed in patients with WD, attributed to overtreatment and resultant Cu depletion, see the IB	Monitoring complete blood count Dose modification (Section 6.6) or discontinuation (Section 7)
Dose-dependent elevations in transaminases (ALT and AST)	Generally mild to moderate in severity, asymptomatic and reversible with dose adjustments were reported, usually after 3-6 weeks of treatment. Results obtained from studies of ALXN1840 and ammonium tetrathiomolybdate in patients with WD; see the IB	Regular monitoring of liver function tests Dose modification (Section 6.6) or discontinuation (Section 7)
Low white blood cell count (leukopenia, bone marrow toxicity)	Leukopenia and bone marrow toxicity (myelosuppression) have been observed in patients with WD, attributed to overtreatment and resultant Cu depletion. Results obtained from studies of ALXN1840 and ammonium tetrathiomolybdate in patients with WD; see the IB	Dose modification (Section 6.6) or discontinuation (Section 7)
Study Procedures and Other		
Liver biopsy: bleeding, infection, liver laceration, pneumothorax, gallbladder injury	Overall rate of serious complications is approximately 1% and mortality at 0.2% Pain is most common complication with one quarter of patients experiencing right upper quadrant or shoulder pain, most common serious complication is bleeding with hemodynamic compromise occurring in 0.01% to 0.5% of cases and includes intraperitoneal hemorrhage, hematoma, and/or hemobilia. Additional complications include but are not limited to transient bacteremia, bile peritonitis, organ injury including pneumothorax (Reddy, 1997 ; Seeff, 2010 ; West, 2010 ; Boyum, 2016)	Abdominal ultrasound is required prior to biopsy to confirm adequate visualization of liver and adjacent structures (Section 5.1) Obese patients (BMI >30 kg/m ²) will be excluded from participating in the study (Section 5.1) Restrictions on antiplatelet and anticoagulant medications (Section 5.3.2) Patients must have a PT-INR < 1.5 (Section 5.2)

Potential Risk of Clinical Significance	Summary of Data/Rationale for Risk	Mitigation Strategy

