4.3. Justification for Dose

For this study, the term “dose” refers to the following:

Dosing for ALXN1840 will be initiated at 15 mg once daily, then the dose will be increased to 30 mg once daily at Week 6.

A starting dose of 15-60 mg daily was shown to have an acceptable safety profile and was effective in reducing NCC in a Phase 2 study in patients with WD (Weiss, 2017). Elevation of hepatic transaminases and/or gamma glutamyl transferase occurred in 39% of patients in the Phase 2 study and were generally associated with higher doses of ALXN1840. Elevations of

liver enzymes were detected by routine laboratory monitoring and were managed by dose reduction or treatment interruption of ALXN1840. In this study, the starting dose will be 15 mg once daily for the first 6 weeks, then the dose will be titrated up to 30 mg once daily. Elevation of liver enzymes, if occurring, and management of other laboratory abnormalities or AEs, will be managed according to [Table 6](#). Any change to dosing in response to laboratory results or AEs must be discussed with the Alexion Medical Monitor and documented in the study record. Subsequent dose increases must be approved by Alexion.

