6.4. Study Drug Compliance

Compliance with ALXN1840 will be assessed by the study team at each study visit. Compliance will be assessed by direct questioning during the site visits and documented in the source documents and case report form (CRF) and checked against the medication returned by the patient. Any deviation from the prescribed dosing regimen including extra doses, missed doses and drug interruptions will be recorded in the electronic data capture (EDC) system.

Patients who take 80% or more of the prescribed doses of ALXN1840 in the first 48 weeks of the study will be considered to have shown acceptable compliance.

Reasons for not following study treatment administration as described in the protocol should be clearly recorded in the source documents.

Once compliance with study drug has been calculated, patients will be dispensed new ALXN1840 to cover dosing requirements until the next in-clinic visit if required.

A record of the number of ALXN1840 tablets dispensed to and taken by each patient must be maintained and reconciled with study drug and compliance records. Study drug start and stop dates, including dates for drug delays and/or dose reductions will also be recorded in the CRF.

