7.3.2.1. Overall Summary of Adverse Events

An overall summary of TEAEs will be presented, including the number of events and the number and percentage of patients experiencing AEs. Percentage will be calculated as $n / N \times 100$, where n is the number of patients with events and N is the number of patients in the Safety Analysis Set. The summary will include categories indicating how many events are TEAEs, treatment-emergent SAEs, and treatment-emergent non-SAEs.

A patient-level listing of all TEAEs will be presented. Separate listings will be produced for SAEs, AEs leading to study drug withdrawal, AEs resulting in death, AEs leading to withdrawal from the study, and pre-treatment AEs (PTAEs).

7.3.2.2. Adverse Events and Serious Adverse Events by System Organ Class and Preferred Term

The number of TEAEs and the number and percentage of patients with events will be presented by SOC and PT. Patients are counted once in each SOC and PT. Percentages will be based on the Safety Analysis Set. The SOCs will be listed in descending frequency as will PTs' within each SOC. If needed, PTs will also be ordered alphabetically.

Treatment-emergent SAEs, treatment-emergent non-SAEs, TEAEs leading to withdrawal of study drug, TEAEs leading to death, and PTAEs will be summarized using the same approach.

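### The SAP tabulates no dose reductions, interruptions or re-challenges, nor the TEAEs leading to them, and its exposure summaries cannot stand in for those counts

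*SAP*

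**What the plan says.** **Protocol.** Section 4.3 reports "Elevation of hepatic transaminases and/or gamma glutamyl transferase occurred in 39% of patients in the Phase 2" study and adds that the raised "liver enzymes were detected by routine laboratory monitoring and were managed by dose reduction or treatment interruption of ALXN1840". Section 2.2.2 says that the elevations "normalized with dose reduction or treatment interruption". Table 3 (section 2.3.1) describes the transaminase rise as dose-dependent. Under section 6.6, patients start at 15 mg daily and move to 30 mg daily at Week 6 (Day 43). Table 6 then sets reductions, temporary interruptions and up to three re-challenges. Section 6.4 says that the dosing record, "including dates for drug delays and/or dose reductions will also be recorded in the CRF".

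**SAP.** Section 5.2 names tolerability of individualized dosing as part of the safety endpoint. Section 7.3.1 plans the following:
- Exposure summary: "Duration of exposure, average daily dose (mg), minimum daily dose (mg), and maximum daily dose (mg) will be summarized using descriptive statistics".
- Duration, "calculated as the last dose of study drug - the first dose of study drug + 1".
- Compliance, as days taken over days expected.
- A by-patient listing of each dose and frequency with dates.

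After the general TEAE tables, section 7.3.2.2 adds serious and non-serious TEAEs and states that "TEAEs leading to withdrawal of study drug, TEAEs leading to death, and PTAEs will be summarized using the same approach". The separate listings in 7.3.2.1 likewise cover withdrawal and death, but not reduction or interruption.

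**The concern.** The plan's response to toxicity is mostly short of permanent withdrawal. A safety summary that counts only withdrawals and deaths therefore misses the commonest planned consequence of a tolerability problem. Safety is a secondary objective, and the obvious questions are how many patients stayed on 30 mg, how many were cut back or paused, and for what. As the SAP stands, no summary table answers them. A drug with frequent toxicity-driven reductions and few permanent stops would look well tolerated in the tables. The exposure summaries might be expected to reveal it, so the check is whether they do.

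**Working it through.** The plan states no dose-modification figure to reproduce, so the check applies the SAP's own exposure definitions to dosing histories.

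**Inputs.** Treatment Period 48 × 7 = 336 days; 15 mg daily on Days 1–42, then 30 mg daily for up to 336 − 42 = 294 days (Protocol 6.6). The five histories are illustrative assumptions using dose steps that appear in Table 6. QOD means every other day. The last dose is taken to fall on Day 336; if a QOD patient's last dose falls on Day 335, duration is one day shorter.

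**Formulas.** Average = total mg ÷ days. Duration = last dose day − first dose day + 1. The SAP does not say whether undosed days enter the average or the minimum, so both readings are shown where they differ.

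| History | Total mg | Average, all 336 days | Average, dosed days | Min, dosed / all days | Max | Duration | Days at 30 mg |
|---|---|---|---|---|---|---|---|
| 1. 15 mg × 42 d, 30 mg × 294 d | 630 + 8,820 = 9,450 | 28.1 | 28.1 | 15 / 15 | 30 | 336 | 294 |
| 2. 15 × 42, 30 × 1, 15 × 293 | 630 + 30 + 4,395 = 5,055 | 15.0 | 15.0 | 15 / 15 | 30 | 336 | 1 |
| 3. 15 × 42, 30 × 126, 15 × 168 | 630 + 3,780 + 2,520 = 6,930 | 20.6 | 20.6 | 15 / 15 | 30 | 336 | 126 |
| 4. 15 × 42, 30 × 196, off 42, 15 QOD over 56 (28 doses) | 630 + 5,880 + 420 = 6,930 | 20.6 | 6,930/266 = 26.1 | 15 / 0 | 30 | 336 | 196 |
| 5. 15 × 42, 30 × 42, off 56, 15 QOD over 196 (98 doses) | 630 + 1,260 + 1,470 = 3,360 | 10.0 | 3,360/182 = 18.5 | 15 / 0 | 30 | 336 | 42 |

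**Reading the table.**
- *Minimum and maximum.* Histories 1, 2 and 3 all give 15 and 30. For anyone who reached 30 mg and was simply reduced to 15 mg daily, the titration fixes both figures.
- *Duration.* All five give 336 days. Net of the interruption, history 5 has 336 − 56 = 280 days, so the SAP figure is 336/280 = 1.20 times as long.
- *Average dose.* It separates history 1 from history 2. Over all days, however, histories 3 (reduction only) and 4 (interruption, then QOD) share the same 20.6 mg. Under the two denominators, history 5 is either 10.0 or 18.5 mg.
- *Compliance.* In history 5, the figure is 182/182 = 100% if paused and alternate days are not expected dosing days, and 182/336 = 54% if they are. The SAP does not say which applies, and 54% falls in none of its three categories, the lowest of which starts at 60%.

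**The case against.** The strongest reply is that the information is not lost. SAP 7.3.1 plans a by-patient dosing listing, which is readable with about 28 patients, and average daily dose moves with down-titration. Maximum dose identifies patients who never took 30 mg. SAP 7.3.3.1 and 7.3.3.2 plan by-visit laboratory summaries, toxicity-grade shift tables, a liver enzyme elevation summary, eDISH plots and liver-test time courses. Because titration is at a fixed visit, Weeks 4 and 6 largely reflect 15 mg and later visits follow the planned increase. All of this stands. A reader might infer that tolerability of 30 mg goes unreported; the documents do not support that. It is reported in pieces and in listings, but not summarised.

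Four further limits also stand:
- The minimum is not always 15. If undosed days count, it is 0 for interrupted and QOD patients.
- A reader might apply the earlier 39% to this trial's enrolment to estimate how many patients will be reduced or interrupted. That figure is a rate of liver-test elevation, including gamma glutamyl transferase, which has no row in Table 6. It came from a study with starting doses of 15–60 mg. It is not a dose-modification rate.
- Splitting all TEAEs by dose at onset is tempting, but dose is confounded with time in a single-arm forced titration, and Table 3 calls only the transaminase rise dose-dependent.
- Protocol 9.4.2 also lists only discontinuation or withdrawal and death, so the SAP does not contradict the protocol.

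What the reply does not answer is that none of these outputs counts patients reduced, interrupted or re-challenged, or links an event to a dose change.

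**Conclusion.** The point holds as a gap in summary reporting. The SAP tabulates neither dose reductions, interruptions and re-challenges nor the TEAEs leading to them, although tolerability of individualized dosing is its stated safety endpoint. The existing exposure summaries do not fill the gap: duration includes days off drug, minimum and maximum are uninformative for a simple 30-to-15 mg daily reduction, and average dose lacks a denominator and cannot separate reduction from interruption.

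The size depends on how many patients are modified, which the documents do not allow one to estimate. The histories above show what the summaries can and cannot distinguish, not how often each will occur. The change should be made, but it does not touch the primary analysis.

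**What to change.** **SAP 7.3.1.**
- Add the number and percentage of patients with at least one dose reduction, interruption and re-challenge, with the reason where it is captured.
- Add the percentage on 30 mg daily at each visit.
- Add duration of exposure net of interruption days, beside the present definition.
- State how undosed and every-other-day dosing days count in the average, the minimum and compliance.
- Keep the overall minimum dose. Replacing it with a minimum after Week 6 would hide earlier reductions.

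**SAP 7.3.2.2.** Add TEAEs leading to dose reduction and TEAEs leading to interruption. Use the AE action-taken field if it is collected with those categories; otherwise link AE dates to dose-change dates.

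**Cost.** SAP wording and a few descriptive tables. Protocol 6.4 puts dates of delays and reductions in the CRF, and missed doses and interruptions in the electronic data capture system, so the core counts need no new data. Two items need confirming: section 6.4 places reasons for departing from the planned administration in source documents, and the AE fields listed in SAP 5.2 and 5.2.1 do not mention action taken. The safety output becomes slightly longer and may look less favourable. No dosing rule changes.
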